9.3.4 Definition of Unexpected Adverse Reaction (UAE)

An adverse reaction, the nature or severity of which is not consistent with the applicable product information (e.g. Product Information/Summary of Product Characteristics). This would include any SAE on health or safety, any life-threatening problem or death caused by, or associated with a drug; or any other unanticipated serious problem associated with a drug that relates to the rights, safety, or welfare of subjects.

9.3.5 Definition of Adverse Events (AE)

Adverse event means any untoward medical occurrence associated with the use of an intervention in humans, whether (or not) considered intervention-related (ICH E6(R2), Section 1.2).

9.3.6 Classification of an Adverse Event

9.3.6.1 Severity of Event

All AEs will be assessed by the study investigator using the CTCAE V. 5.0. Investigator or qualified designee will assess the severity of AEs using the following categories:

- Grade 1: Mild; asymptomatic or mild symptoms; clinical or diagnostic observations only; intervention not indicated.
- Grade 2: Moderate; minimal, local or noninvasive intervention indicated
- Grade 3: Severe or medically significant but not immediately life-threatening; hospitalization or prolongation of hospitalization indicated
- Grade 4: Life-threatening consequences; urgent intervention indicated.
- Grade 5 Death related to AE.

9.3.6.2 Relationship to Study Intervention

Relationship to Study Products: All AEs must have their relationship to study intervention assessed by the investigator or qualified designee who examines and evaluates the subject based on temporal relationship and his/her clinical judgment. The degree of certainty about causality will be graded using the categories below.

Definitely:	The relationship of the AE and the drug or the study procedure can be established.
Probably:	While a clear relationship to the drug or to the study procedure cannot be established, the AE is associated with an expected AE or there is no other medical condition or intervention, which could explain the occurrence of such an event.
Possibly:	There is no clear relationship between the AE and the drug or study procedure; however, one cannot conclude that there is no relationship.
Unrelated:	There is no relationship between the AE and the drug or study procedure. This may include but is not limited to the incident being an expected outcome of a previously existing or concurrent disease, concomitant medication or procedure the subject experienced.

9.3.7 Expectedness

Study Team members who are clinically qualified (e.g., a physician, co-Investigator, sub-Investigator) will be responsible for determining whether an AE is expected or unexpected. An AE will be considered unexpected if the nature, severity, or frequency of the event is not consistent with the risk information previously described for the study products. This information will be provided to the IRB/IEC, and to any relevant governmental agency with regulatory or public health authority.

9.3.8 Time Period and Frequency for Event Assessment and Follow-Up

The occurrence of an AE or SAE may come to the attention of study personnel during study visits and interviews of a study subject presenting for medical care.

9.3.9 Capturing AEs

All AEs including local and systemic reactions not meeting the criteria for SAEs will be captured on the appropriate CRF. Information to be collected includes event description, time of onset, investigator's assessment of severity, relationship to study product (assessed only by those with the training and authority to make a diagnosis), and time of resolution/stabilization of the event. All AEs occurring while on study must be documented appropriately regardless of relationship. All AEs will be followed to adequate resolution.

9.4 Adverse Event Reporting

Adverse event data will be summarized for all subjects in the safety population. Serious adverse events and unexpected adverse drug reactions will be summarized as subject-based counts and percentages by AE category. In addition, subject listings will be provided for serious, unexpected, and unanticipated adverse reactions. Any adverse events leading to discontinuation of study drug or death will also be listed for all subjects.

9.4.1 Serious Adverse Event Reporting

Study team members who are qualified will immediately report any serious adverse event, whether or not considered study intervention related, including those listed in the protocol and must include an assessment of whether there is a reasonable possibility that the study intervention caused the event. Study endpoints that are SAEs must be reported in accordance with the protocol. Refer Section of Unanticipated Problems provides further detail.

9.4.2 Reporting Events to IRB/IEC

AEs, SAEs and Unanticipated problems (UPs) will be reported to IRB/IEC.

9.4.3 Events of Special Interest

N/A

9.4.4 Reporting of Pregnancy

Favipiravir has the potential for teratogenicity. In nonclinical reproductive and developmental toxicity studies, favipiravir was shown to be teratogenic in multiple animal species (mice, rats, rabbits and monkeys). Pregnancy status will be collected at the time of enrollment. Pregnancy testing for women of child bearing potential will occur on study days 1, 7 And 28. Any pregnancy that occurs during study days 1-28 will be followed, until the end, and reported to FDA and other regulatory authorities, where required.

9.5 Unanticipated Problems (UPs)

9.5.1 Definition of Unanticipated Problems (UPs)

The Office for Human Research Protections (OHRP) considers unanticipated problems involving risks to subjects or others to include, in general, any incident, experience, or outcome that meets all the following criteria:

- Unexpected in terms of nature, severity, or frequency given (a) the research procedures that are described in the protocol-related documents, such as the Institutional Review Board (IRB)/Independent Ethics Committee(IEC) approved research protocol and informed consent document; and (b) the characteristics of the subject population being studied;
- Related or possibly related to participation in the research (“possibly related” means there is a reasonable possibility that the incident, experience, or outcome may have been caused by the procedures involved in the research); and
- Suggests that the research places subjects or others at a greater risk of harm (including physical, psychological, economic, or social harm) than was previously known or recognized.

9.5.2 Unanticipated Problem Reporting

The investigator will report unanticipated problems (UPs) to the reviewing IRB/IEC. The UP report will include the following information:

1. Protocol identifying information: protocol title and number, PI's name, and the IRB/IEC project number;
 - A detailed description of the event, incident, experience, or outcome;
 - An explanation of the basis for determining that the event, incident, experience, or outcome represents an UP;
 - A description of any changes to the protocol or other corrective actions that have been taken or are proposed in response to the UP.
2. To satisfy the requirement for prompt reporting, UPs will be reported using the following timeline:
 - UPs that are SAEs will be reported to the IRB/IEC within 10 working days of the investigator becoming aware of the event.
 - A Study Team evaluation of an UP will be performed with a report of results of such evaluation will be provided to the reviewing IRB/IEC by the PI within 10 working days.

9.5.3 Reporting Unanticipated Problems to Subjects

Subjects will be informed about UPs, and study-related results on an individual or aggregate level.

10.0 STATISTICAL CONSIDERATIONS

10.1 Statistical Hypotheses

The primary efficacy objective of this study is to demonstrate that treatment with favipiravir in subjects with COVID-19 and mild-to-moderate symptoms will shorten the time to sustained clinical recovery ("component of the clinical outcome"). Primary efficacy endpoint: Time to sustained clinical recovery, defined as the time (number of days) from the start of the study treatment until symptom relief, evaluated from study day 1 onward.

10.2 Sample Size Considerations

10.2.1 Sample Size Determination: study's primary endpoint: time to sustained clinical recovery by Study Day 28

Group sample sizes of approximately 625 in each treatment group (Favipiravir and placebo) to get at least 815 clinical recoveries will achieve sufficient power to detect a clinically meaningful effect size using a two-sided Wilcoxon test at an overall significance level of 0.05.

10.2.2 Sample Size Justification: study's primary endpoint: time to sustained clinical recovery by Study Day 28

A review of the medical literature including descriptive and intervention studies reveals variation in the estimate of 'median time to symptom alleviation'. There is lack of consistency among studies in regard to: 1) the definition used for 'symptom alleviation', 2) the reference time point (some use the day of first symptoms, the day of first positive PCR test, the day of study enrollment, and the day of hospitalization, 3) the length of follow up. To account for the uncertainty surrounding the estimate of 'median time to symptom alleviation', we performed a series of intermediate sample size calculations for a variety of likely scenarios with median times to sustained clinical recovery for the control group ranging from 3 to 15 days and median times to sustained clinical recovery for the favipiravir group ranging from -1 to -6 days (when possible) as compared to the control group. The worst case of those scenarios was retained to establish the definitive sample size estimation for the trial.

The definitive sample size assessment is based on a group sequential design with a possibility to stop for efficacy and for futility (unbinding rule) at interim, once 45% of the information is obtained (i.e. 367 events), using Power family ($\Phi=1.147$) alpha and beta spending functions. Assuming proportional hazards, a median time of 5 days in the control group vs. a median time of 4 days in the favipiravir group (which provide a hazards ratio of 1.25) and controlling for an overall alpha of 5% (two-sided), it is estimated that about 475 participants per group would be required to obtain a total of **815 clinical events** (defined as clinical recoveries). This will ensure a power of 85% to detect a difference between the two groups in terms of time to clinical recoveries by Day 28.

The unbinding futility rule uses a Power family beta spending function with $\Phi=1.147$ and the probability to stop for futility at interim when there is no difference between the two groups (i.e. $HR=1$) is 73%.

The test for efficacy at interim uses a Power family alpha spending function with $\Phi=1.147$ and if the hazard ratio is truly 1.25, the probability to conclude efficacy at interim is 49%.

This is to be noted that the futility rule is unbinding and that the recommendations whether or not to stop for futility will be done by the Data and Safety Monitoring Board (DSMB) (see section 5.5), upon review of the safety and efficacy data, and not solely based on the futility rule.

10.2.3 Sample Size Determination: Sub-study's Viral Shedding Endpoint: Time to undetectable viral shedding by study day 10

Group sample sizes of approximately 275 subjects in each treatment group (Favipiravir and placebo) in order to obtain 112 undetectable viral shedding events will achieve sufficient power to detect a clinically and epidemiologically meaningful effect size using a two-sided Wilcoxon test at a significance level of 0.05.

10.2.4 Sample Size Justification: Sub-study's Viral Shedding Endpoint: Time to undetectable viral shedding by study day 10

To calculate the required sample size, we used the following assumptions: 1) Follow-up duration per patient of 10 days, 2) Alpha of 0.05, 3) Lost to follow up of 0, 4) Exponential survival rates, 5) Median

time to sustained clinical recovery for the control group of 5 days, 6) Median time to sustained clinical recovery for the favipiravir group of 2.9 days.

In order to detect as statistically significant difference in the median time to undetectable viral shedding of 5 vs. 2.9 days in the control vs. favipiravir group, respectively (HR = 1.7), it is estimated that a total of about 550 subjects (275 per treatment group) in order to obtain 112 clinical events defined as undetectable viral shedding events would be required to achieve a power of 80%.

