10.4 Statistical Analyses: General Approach

Baseline demographic and clinical characteristics and other results will be summarized using descriptive summary statistics. Data collected in the trial will be summarized overall and by treatment arm.

Survival analysis techniques will be used to analyze the time-to-event variables. Failure curves will be constructed for time to positive event using Kaplan-Meier estimates. Time to sustained clinical recovery will be compared using a Gehan Wilcoxon test which gives more weight to early events. Time to a negative event (such as time to death, time to hospitalization) will be compared using the Log-rank test for comparison of survival distributions. Summary tables for safety and efficacy endpoints will include event rates (Kaplan-Meier estimates of event rates), relative risk, confidence interval for the relative risk, the difference in means/rates, the confidence interval for difference in means/rates, and the p-value.

For categorical variables, results within each arm will be summarized with subject counts, percentages, and 95% confidence intervals. The differences between the two treatment arms will be summarized with the difference in percentages and the asymptotic 95% confidence interval for the difference of two percentages.

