10.5 Analysis of the Primary Efficacy Endpoint(s)

For the primary efficacy endpoint, time to sustained clinical recovery from study day 1 onward will be compared using a Gehan Wilcoxon test.

The primary analysis of the primary efficacy endpoint will be based on the Modified Intent to Treat Population (mITT), defined as any subject randomized into the study and took at least one dose of study medication (excluding subjects who qualified for enrollment based upon changes in taste and smell).

Additional primary efficacy endpoint analyses will also be performed using the mITT, mITT2, and the Per Protocol populations. Every effort will be made to ensure that subjects are followed until hospitalization, death, or 28 days post treatment start, whichever happens first. Subjects who were hospitalized or died will be assumed to have not met the primary endpoint in the primary analysis.

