10.8.2 Planned Interim Analyses

The DSMB will also review the results of the first interim analysis for futility and efficacy once 45% of the clinical events (i.e. 367 clinical recoveries) are obtained and once 45% of the patients are recruited.

The nominal alpha of 0.02 and of 0.0369 at the time of interim and final analysis, respectively. A p-value less than 0.02 (interim) or 0.0369 (final) will be considered to be statistically significant.

Futility will be concluded at interim on the primary efficacy endpoint if Z-value is smaller than 0.58964 (i.e. p-value is larger than 0.6389).

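### Section 10.2.2: the 85% power at 815 events is a log-rank figure, while the planned Gehan Wilcoxon test gives about 78–82% there (futility followed); the worst-case claim is unsupported by the ranges given

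*Combined protocol and SAP*

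**What the plan says.** Section 10.2.2 explains that published medians vary, so "we performed a series of intermediate sample size calculations for a variety of likely scenarios". The control side is described as "median times to sustained clinical recovery for the control group ranging from 3 to 15 days"; the favipiravir side is described as "ranging from -1 to -6 days (when possible) as compared to the control group". It then says: "The worst case of those scenarios was retained to establish the definitive sample size estimation for the trial". The case carried forward is 5 vs 4 days, hazard ratio 1.25, under proportional hazards. There is one interim look at 367 events and a final total of 815, reached with about 475 participants per group. Of that design it says: "This will ensure a power of 85% to detect a difference between the two groups". No test is named beside the 85%.

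Section 10.2.1 and the synopsis tie 815 recoveries to about 625 per group. Section 10.2.1 says at least 815 and names a two-sided Wilcoxon test. The analysis sections are specific. Section 10.4: "Time to sustained clinical recovery will be compared using a Gehan Wilcoxon test which gives more weight to early events". Section 10.5: "time to sustained clinical recovery from study day 1 onward will be compared using a Gehan Wilcoxon test".

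Section 10.8.2 sets nominal two-sided levels of 0.02 (interim) and 0.0369 (final), and adds: "Futility will be concluded at interim on the primary efficacy endpoint if Z-value is smaller than 0.58964". Section 10.2.2 describes the futility rule as one the monitoring board need not follow.

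**The concern.** Under proportional hazards the log-rank test is the efficient choice, and a test that weights early events loses power at the same number of events. If the 85% comes from a log-rank calculation, it is not the power of the test that will be run. The size of the loss depends on how many subjects never recover, and section 10.2.2 does not give that.

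The worst-case sentence tells the reader that uncertainty about the medians was covered by sizing for the most demanding scenario. If harder cases lie inside the ranges quoted, that assurance fails as written.

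The same 815 events go with both 475 and 625 per group, with no recovery or attrition rate. A reader therefore cannot tell at what event count the trial is expected to finish, and the Gehan power depends heavily on it.

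**Working it through.** **Inputs.** Hazard ratio 1.25, looks at 367 and 815 events (45% information), 475 per group: section 10.2.2. About 625 per group: section 10.2.1. Nominal levels 0.02 and 0.0369, futility Z < 0.58964: section 10.8.2. Allocation 1:1: section 7.3. Efficacy bounds: Z = 2.326 and 2.087.

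**Step 1: reproduce the 85%.** The log-rank drift at the final look is ln(1.25) × √(815/4) = 0.2231 × 14.27 = 3.185. A two-look normal calculation with these bounds gives 84.8% with futility followed and 87.1% with it ignored. The stated 85% is therefore the log-rank power with futility followed.

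**Step 2: the planned test.** Under proportional hazards, with a share c not recovered but at risk to Day 28, the efficiency of Gehan relative to log-rank is

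ARE = [(1 − c²)/2]² / {[(1 − c³)/3] × (1 − c)}.

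The Gehan drift is the log-rank drift times √ARE. Keeping non-recoverers at risk follows sections 4.0 and 10.5: subjects who die or are hospitalised count as not having met the endpoint, and lost subjects whose status cannot be confirmed take the worst outcome. The documents give no value for c. The values below come from the documents' own sizes.

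| Case at 815 events | c | ARE | Gehan drift | Power, futility followed / ignored |
|---|---|---|---|---|
| 815 of 950 recover | 0.142 | 0.842 | 2.922 | 78.2% / 80.9% |
| 815 of 1,250 recover | 0.348 | 0.928 | 3.068 | 82.0% / 84.5% |

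Simulation of both tests on whole-day times (60,000 trials per case) agrees: Gehan 78% / 81% and 82% / 84–85%, against log-rank 85% / 87% in the same runs.

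**Step 3: the event count.** With exponential medians of 5 and 4 days, recovery by Day 28 is 1 − 2^(−28/5) = 0.979 and 1 − 2^(−28/4) = 0.992, mean 0.986. That gives 950 × 0.986 ≈ 936 events or 1,250 × 0.986 ≈ 1,232 events, not 815. At 1,232 events the log-rank drift is 0.2231 × √(1,232/4) = 3.916. With c = 0.014, ARE is 0.760 and the Gehan drift 3.415, giving 89.3% / 91.3% (simulated 89.2% / 91.4%). At 936 events the simulated figures are 79.6% / 82.2%.

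**Step 4: the worst case.** Taking the hazard ratio as the ratio of medians, as section 10.2.2 does, and crossing whole-day control medians 3–15 with reductions 1–6 (favipiravir median at least 1 day) gives 68 pairs. Fifteen have a hazard ratio below 1.25: ten with a one-day reduction and five with a two-day reduction. Log-rank power at 815 events, futility followed:

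| Medians (days) | Hazard ratio | Power |
|---|---|---|
| 5 vs 4 | 1.25 | 84.8% |
| 6 vs 5 | 1.20 | 68% |
| 10 vs 9 | 1.11 | 28% |
| 15 vs 14 | 1.07 | 14% |

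**The case against.** **The trial may still have adequate power.** Section 10.2.1 says at least 815, enrolment is about 1,250, and no passage makes the 815th event the trigger for the final analysis. At the enrolled size the Gehan figures run from 82% / 84.5% (815 events) to about 89% / 91% (1,232 events), on both sides of 85%. The futility rule is also non-binding; with it ignored and 815 of 1,250 recovering, Gehan is within a point of the stated figure. All of this stands. A reader might infer that the trial is underpowered, and the documents do not support that. What remains is that the stated 85% belongs to another test. On the basis where it reproduces (futility followed), the gap at 815 events is about 3 to 7 points.

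**A larger shortfall is tempting but not planned.** Gehan power falls to about 73% / 76% only with near-complete recovery in about 413 per group, or with heavy random censoring. No section plans 413 per group. Random censoring strong enough to leave 815 events (0.0243 or 0.0822 per day) would censor 49% or 90% of subjects still at risk by Day 28, and conflicts with how sections 4.0 and 10.5 treat lost, hospitalised and deceased subjects.

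**The futility bound is weak evidence about the test.** Beta spent at 45% is 0.15 × 0.45^1.147 = 0.060. With log-rank drift 2.137 at 367 events, the bound is 2.137 − 1.555 = 0.583, near the stated 0.58964. But section 10.8.2 equates that Z with a p-value of 0.6389, whereas Z = 0.58964 is two-sided p = 0.555 and p = 0.6389 is Z = 0.469, a value the Gehan test could produce. Because the bound contradicts itself, the attribution to log-rank rests on Step 1.

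**The scenarios actually run may not include harder cases.** The 68-pair cross is one reading of the ranges. A set such as 3 vs 2, 5 vs 4, 10 vs 8, 15 vs 12 and 15 vs 9 spans both ranges with a smallest hazard ratio of 1.25. So the documents do not prove the sentence false for the set that was run. They list no set, so the claim cannot be supported as written.

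**Conclusion.** The concern holds in two limited forms.

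First, 85% at 815 events is a log-rank power, not the power of the planned Gehan Wilcoxon test. That power is about 78% / 81% (futility followed / ignored) for 815 of 950 recovering and about 82% / 84.5% for 815 of 1,250. These figures assume proportional hazards at 1.25, exactly 815 events, and non-recoverers at risk to Day 28. The non-recovery shares are assumptions inferred from the documents' sample sizes. Proportional hazards matters: if an equal share of each arm never recovers and the 1.25 applies only to the rest, both tests fall well below these figures and Gehan is no longer the weaker one. The error is in the stated figure and in the missing link between subjects and events; it is not evidence that the trial is too small.

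Second, 5 vs 4 days is not the hardest case within the ranges as written, so the worst-case statement is unsupported until the scenarios are shown.

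**What to change.** In section 10.2.2:

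- Replace the 85% with simulated Gehan Wilcoxon power under the two-look design, handling hospitalised, deceased and unresolved lost subjects as sections 4.0 and 10.5 do. Report it at 815 events and at the expected event count for 1,250 subjects, and say whether the futility rule is followed.
- State the Day 28 recovery and attrition assumption that links 475 per group, 625 per group and 815 events.
- Replace the worst-case sentence with: *The design targets a hazard ratio of 1.25 (medians 5 vs 4 days).*

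The cost is protocol and SAP wording and one simulation. The stated power at 815 events becomes slightly less favourable. No change to sample size, test or endpoint is needed.

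### The 85% power at 815 recoveries is a log-rank figure, but the planned Gehan-Wilcoxon test gives about 78-81% for 815 of 950, and the 49% chance of interim efficacy is too high for either test

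*Combined protocol and SAP*

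**What the plan says.** - **Section 10.2.2, derivation:** "Assuming proportional hazards, a median time of 5 days in the control group vs. a median time of 4 days in the favipiravir group", that is HR 1.25. Then "it is estimated that about 475 participants per group would be required to obtain a total of" 815 events, followed by "This will ensure a power of 85% to detect a difference between the two groups".
- **Section 10.2.2, design:** one interim look at 45% information (367 events), power-family alpha and beta spending with parameter 1.147, and a non-binding futility rule. If the HR is 1.25, "the probability to conclude efficacy at interim is 49" per cent. If the HR is 1, the chance of a futility stop is put at 73%.
- **Section 10.2.1:** about 625 subjects per group are to be enrolled "to get at least 815 clinical recoveries", and this "will achieve sufficient power to detect a clinically meaningful effect size using a two-sided Wilcoxon test at an overall significance level of 0.05".
- **Section 10.8.2:** nominal levels 0.02 and 0.0369, futility if Z is below 0.58964, and a second condition for the look, that 45% of patients have been recruited.
- **Sections 10.4 and 10.5:** "Time to sustained clinical recovery will be compared using a Gehan Wilcoxon test which gives more weight to early events". For the primary endpoint, time to recovery "will be compared using a Gehan Wilcoxon test".

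Section 10.2.2 does not say which test's information lies behind the 85%.

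**The concern.** Under proportional hazards the log-rank test is the efficient one. Gehan-Wilcoxon, by weighting early events, needs more events for the same power. A power calculated with log-rank information therefore overstates what the planned test delivers. If that happened here, the trial runs a larger risk than the stated 15% of missing the effect it was sized for.

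The 49% matters for a different reason. It is the stated chance of an efficacy result at the look that the DSMB will review, and it can be checked directly from the plan's limits.

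**Working it through.** **Inputs.** HR 1.25, 815 events, 950 subjects and a look at 367 events (10.2.2); two-sided levels 0.02 and 0.0369, so critical Z 2.326 and 2.087, and futility Z < 0.58964 (10.8.2); 1:1 allocation (7.3). Information fraction 367/815 = 0.450; correlation between looks √0.450 = 0.671.

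**1. Reproduce the 85%.** Log-rank drift is ln(1.25)·√(D/4).
- Final: 0.2231·√(815/4) = 3.185. Interim: 0.2231·√(367/4) = 2.137.
- Power = P(Z₁ > 2.326) + P(0.58964 < Z₁ ≤ 2.326, Z₂ > 2.087) = 84.8%. Dropping the futility limit gives 87.1%.

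So the stated 85% is the log-rank value with futility followed.

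**2. Second check on the source.** The stated beta spending at the look is 0.15·0.45^1.147 = 0.0600. For P(Z₁ < 0.58964) = 0.0600 the interim drift must be 0.58964 + 1.555 = 2.144. By log-rank that is 4·(2.144/0.2231)² = 369 events, against 367 stated. By Gehan-Wilcoxon it would be about 398 to 489, depending on the share who recover.

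**3. Gehan-Wilcoxon.** With HR 1.25 for the whole population and a share s still unrecovered and at risk to Day 28, efficiency relative to log-rank is 3(1−s²)²/[4(1−s³)(1−s)].
- 815 of 950: s = 135/950 = 0.142, efficiency 0.842.
- Final drift 3.185·√0.842 = 2.92; interim drift 2.137·√0.842 = 1.961.

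Results at 815 recoveries:

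| Test and setting | Power, futility followed | Power, futility ignored | Interim efficacy at 367 |
|---|---|---|---|
| Log-rank | 84.8% | 87.1% | 42.5% |
| Gehan, 815 of 950 | 78.2% | 80.8% | 35.7% |
| Gehan, 815 of 1250 (s = 0.348, efficiency 0.928) | 82.0% | 84.5% | 39.4% |
| Gehan, exponential times, 815 of about 827 | 73.6% | 76.4% | 31.9% |

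Simulation with whole-day times (8,000 trials per setting) agrees for Gehan-Wilcoxon: 78.1%/80.7% and 35.3% for 950; 82.7%/84.8% and 39.7% for 1250; 74.3%/76.6% and 32.2% for exponential times with 828 subjects.

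Other assumptions give less:
- Random or early dropout down to 815 of 950: about 73-78% power, interim efficacy about 32-33%.
- A share of each arm never recovers and HR 1.25 applies only to recoverers: about 57-60% (815 of 950) or 33-34% (815 of 1250).

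**4. The 49%.** Under HR 1.25 at 367 events:
- Log-rank efficacy: P(Z₁ > 2.326) with drift 2.137 = 42.5%. Log-rank futility: P(Z₁ < 0.58964) = 6.1%. Sum 48.6%.
- Gehan-Wilcoxon, 815 of 950: efficacy 35.7%, futility 8.5%.

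Under HR 1, P(Z₁ < 0.58964) = 72.2% for either test; adding the 1.0% chance of an efficacy stop gives 73.2%. The stated 49% and 73% therefore both match the log-rank probability of stopping for either reason.

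**5. What enrolment of 1250 does.** At the 815/950 ratio, 1250 subjects give about 1,072 recoveries, and Gehan power is about 84-91% depending on when the look falls. It reaches 85% at about 974 recoveries (about 1,136 subjects) with futility followed, or 910 (about 1,061) with it ignored.

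**The case against.** **The trial enrols 1250, not 950.** Sections 2.1, 5.1 and 10.2.1 all give about 1250 or 625 per group, and futility is non-binding. On 815 of 1250 with futility ignored, Gehan power is 84.5%, close to 85%. This stands as mitigation. But the 85% sentence is attached to about 475 per group, and the like-for-like log-rank value with futility ignored is 87.1%.

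**The 78-81% rests on an assumed censoring pattern.** This is true. Exponential medians of 5 and 4 days leave only about 1.4% unrecovered at Day 28, so 14% unrecovered implies a recovery rate that slows. Section 4.0 treats unresolved losses to follow-up as the worst outcome, and section 10.5 counts hospitalised or deceased subjects as not recovered, but neither gives a censoring time. The figure needs its range beside it. None of the settings examined gives 85% at 815 recoveries with futility followed.

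**The futility limit contradicts itself.** Sections 2.1 and 10.8.2 equate Z = 0.58964 with p = 0.6389. Two-sided, that Z gives p = 0.555, and that p gives Z = 0.469. With 0.469, step 2 returns 329 log-rank events, or 355 to 391 for Gehan-Wilcoxon, and no longer separates the tests. The stated 73% favours the Z value (72.2% against 68.1%), and step 1 with futility ignored does not use the limit at all.

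**The look may come later than 367 events.** With the 45%-recruited condition (about 563 subjects), Gehan interim efficacy is about 41% at 439 recoveries (180-day accrual assumed) and 47% at 483 (all 563 followed to Day 28). It reaches about 49% only if nearly all 563 are followed and recover (555). Section 10.2.2 ties its 49% to a look at 367.

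**Type I error.** The choice of test for the power calculation does not affect it. But a look at 367 followed by a final analysis at 1,072 with the stated 0.02 and 0.0369 gives about 5.17% overall. The lower end of the 84-91% above therefore uses a final level of 0.0351.

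**Conclusion.** The concern holds. At 815 recoveries the stated 85% is a log-rank result. The planned test gives about 78-81% for the plan's own 815 of 950, so the risk of missing the assumed effect is about 19-22% rather than 15%. This assumes proportional hazards, HR 1.25 for the whole population and non-recoverers at risk to Day 28. It applies only if the final analysis is made near 815 recoveries.

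The 49% overstates the chance of an efficacy result at 367 events by about 6 points (log-rank) or 13 points (Gehan-Wilcoxon). The log-rank part of that does not depend on the censoring assumption. That 49% and 73% are mislabelled total stopping probabilities is an inference from how closely they match. That 49% is not the efficacy probability at 367 events is arithmetic.

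The point should be corrected, because these figures describe how the interim look and final test will perform. It does not show the trial to be too small.

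**What to change.** In sections 10.2.1 and 10.2.2 and the synopsis:

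1. Name the test behind the 85%.
2. Restate power at 815 recoveries for Gehan-Wilcoxon, about 78-81% for 815 of 950, with the three assumptions above. Give the range: 74-76% if almost all recover, 82-85% for 815 of 1250, and lower with dropout or if the effect applies only to recoverers. The sponsor should recompute this with its own censoring assumption stated.
3. Replace the 49% with the efficacy-only probability for Gehan-Wilcoxon at 367 events (about 36% for 815 of 950; 32-39% across the settings in the table), or relabel it as the log-rank chance of stopping for efficacy or futility. Label the 73% the same way (72% for futility alone). Note that the recruitment condition in 10.8.2 may delay the look and raise the efficacy figure.
4. If the plan relies on more than 815 recoveries to restore power, say so and recompute the final level from the information fraction actually used.

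The cost is wording and a less favourable stated power. Items 1 to 3 need no extra patients and no change to the stopping limits.
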